#### 14.2.1 Tolerability Parameters

Parameters	Value
Burning	It should be recorded as absent on 95% of the evaluated subjects
Foreign body sensation	It should be recorded as absent on 95% of the evaluated subjects
Tearing	It should be recorded as absent on 95% of the evaluated subjects
Secretion	It should be recorded as absent on 95% of the evaluated subjects
Conjunctival hyperemia	
The following must be accomplished:
 
 
• Absent: <math>\geq 95.0\%</math>
 
• Mild: <math>\leq 5.0\%</math>
 
• Moderate: <math>\leq 2.5\%</math>
 
• Serious: <math>\leq 1.0\%</math>
 

Photophobia	
The following must be accomplished:
 
 
• Absent: <math>\geq 95.0\%</math>
 
• Mild: <math>\leq 5.0\%</math>
 
• Moderate: <math>\leq 2.5\%</math>
 
• Serious: <math>\leq 1.0\%</math>
 

Safety variables of the study drug PRO-087 will be evaluated in the visits indicated in the schedule, using the following parameters:

1. Best-corrected visual acuity
2. Intraocular pressure
3. Ocular surface
4. Anterior segment exploration
5. Posterior segment exploration
6. Tear film break-up time
7. Schirmer test
8. Corneal depithelization
9. Adverse events

It is considered that the drug in evaluation PRO-087 is tolerable for use in human beings, if there are not changes on the marked parameters (14.3.1) by more than 5% of subjects, in both eyes, in compliance with all visits and adherence to treatment at an  $\geq 80\%$  during the time of study assessment.

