## 13. Sample size determination

---

The sample size was calculated according to the 3 major safety variables. The variable is considered the largest number of subjects obtained as the sample size required to meet the objectives of the study.

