#### 14.2 Tolerability Evaluation

Tolerability variables of the study drug PRO-087 will be evaluated in the visits indicated in the schedule, using the following parameters:

1. Burning
2. Foreign body sensation

3. Tearing
4. Conjunctival hyperemia
5. Pruritus
6. Photophobia
7. Tear secretion

It is considered that the drug in evaluation PRO-087 is tolerable for use in human beings, if there are no changes on the marked parameters (14.1.2) by more than 5% of subjects, in both eyes, in compliance with all visits and adherence to treatment at an  $\geq 80\%$  during the time of study assessment.

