#### 14.3.1 Safety Parameters

Parameters	Value
Best-corrected visual acuity	No change of 1 line in the Snellen chart or 1 logarithmic point (logMAR)
Intraocular pressure	Measurements below 7 mmHg and over 21 mmHg
Corneal depithelization	Percentage of the damaged epithelium of the ocular surface, reduction of staining according to the Oxford scale.
Anterior segment examination	Abnormalities on any of the comprised structures: Cornea, iris, pupil, iris-corneal angle and crystalline.
Posterior segment examination	Abnormalities on any of the comprised structures: Vitreous, retina, macula and optic nerve.
Tear film break-up time	Reduction of more than 20% over the baseline time.
Schirmer test	Reduction of more than 20%
Adverse events	Presence of adverse events modifying some of the abovementioned criteria or others evaluated as serious.
OSDI	Increase of the score of more than 10 points.

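### Section 14 gives two rules that both conclude PRO-087 is tolerable, one of them on the efficacy table, and no rule that concludes on safety, so as written the verdicts can contradict each other

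*Combined protocol and SAP*

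**What the plan says.** Section 14 contains three decision rules, each with a limit of 5% of subjects.

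- **14.1 (efficacy).** PRO-087 is effective if the changes in table 14.1.2 appear in more than 5% of subjects in both eyes. Apart from the adverse events row, the rows of that table describe improvement; for TBUT, a rise of 30% from baseline or a value of at least 10 seconds.
- **14.2 (tolerability).** The section lists seven symptoms and signs, then calls the product "tolerable for use in human beings, if there are no changes on the marked parameters (14.1.2) by more than 5% of subjects". Table 14.1.2 is the efficacy table. The tolerability table is 14.2.1, which follows directly.
- **Safety rule, after table 14.2.1.** It opens with "Safety variables of the study drug PRO-087 will be evaluated in the visits indicated in the schedule", lists nine variables and ends: "PRO-087 is tolerable for use in human beings, if there are not changes on the marked parameters (14.3.1". Table 14.3.1 is titled Safety Parameters.

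The third item of the safety list is "3. Ocular surface", which has no row of its own in table 14.3.1. OSDI is not in the list, but the table has an OSDI row: "Increase of the score of more than 10 points". Section 13 opens by saying "The sample size was calculated according to the 3 major safety variables", and OSDI is one of the three.

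**The concern.** Objective 5.2.1 is to evaluate safety, and the study title promises efficacy and safety. The only verdicts that section 14 can return are effective and tolerable, the latter by two routes. If the rules are followed as written, the report could state both that PRO-087 is tolerable and that it is not, with no stated order of precedence. It could also declare the product effective and not tolerable on the same improvement in the same subjects. Someone would then have to choose, after seeing the data, which rule carries the conclusion. The mismatch between the safety list and its table adds a smaller doubt about which variables belong to the safety assessment.

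**Working it through.** The plan states no figure on this point, so there is none to reproduce. The check is a comparison of the rules, with a count attached.

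**1. Rules side by side**

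| Rule | Verdict word | Table cited | TBUT entry in that table |
|---|---|---|---|
| 14.1 | effective | 14.1.2 (efficacy) | rise of 30%, or at least 10 s |
| 14.2 | tolerable | 14.1.2 (efficacy) | rise of 30%, or at least 10 s |
| Safety variables | tolerable | 14.3.1 (safety) | fall of more than 20% |

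The first two rows use the same table with opposite conditions. More than 5% of subjects showing the change is required for effective and rules out tolerable. On those parameters the two verdicts exclude each other.

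**2. The 5% limit as a count.** Section 13.3 gives 96 per group, or 80 before the allowance for losses. 4/96 = 4.2% and 4/80 = 5.0%, neither above 5%. 5/96 = 5.2% and 5/80 = 6.25%, both above. At either size, five subjects exceed the limit.

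**3. A worked case.** Suppose 5 of 96 subjects have TBUT up 30% in both eyes and nobody has a fall.
- 14.1: 5.2% show the TBUT change, so they count towards effective.
- 14.2: 5.2% show a change listed in 14.1.2, so the product is not tolerable.
- Safety rule: no subject has a fall of more than 20%, so the TBUT row is not breached and, on that row, the product is tolerable.

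This takes *changes* to mean those described in the value column of the cited table.

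**4. How often this could happen.** The documents give no rates, so these are assumptions for a single parameter. Let p_i be the share improving enough for 14.1.2 and p_w the share worsening enough for 14.3.1. The two are mutually exclusive, so

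P(14.2 fails, safety rule passes) = Σ over w = 0 to 4 of Bin(w; n, p_w) × P[Bin(n − w, p_i/(1 − p_w)) ≥ 5].

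| p_i | p_w | n = 96 | n = 80 |
|---|---|---|---|
| 10% | 2% | 0.93 | 0.89 |
| 30% | 2% | 0.96 | 0.98 |
| 30% | 3% | 0.84 | 0.91 |

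**5. Safety list against table 14.3.1.** Each has nine entries and eight are shared. Only in the list: ocular surface. Only in the table: OSDI. The nearest table row to ocular surface is corneal depithelization, but the list carries that separately as item 8.

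**The case against.** The strongest reply is that these are copying slips. The second rule is introduced as being about safety variables and cites the safety table, with thresholds and a 5% limit. A safety criterion therefore exists and only its verdict word is wrong. Likewise, 14.2 plainly meant its own table: 14.2.1 asks for most symptoms to be absent in 95% of subjects, which matches a 5% limit. Read that way, passing safety and failing tolerability is two domains differing, not a contradiction. This is a fair account of the probable intent and it limits the severity. It does not remove the point, because both slips are in the operative text of decision rules.

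A reader might go further and infer that the safety verdict flips according to whether the list or the table is followed for OSDI. The documents do not support that: the rule names table 14.3.1, so OSDI counts. Nor is section 13's description of OSDI as a safety variable strong support, since 13.3 says that Schirmer, another of the three, is used to demonstrate efficacy.

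It is also tempting to size the OSDI row. Taking the SD of 6.4 in section 13.2 as the SD of change, with normality and zero mean change, 1 − Φ(10/6.4) = 5.9% of subjects worsen by more than 10 points. The chance of five or more is then 51% at n = 80 and 68% at n = 96. This is unstable: 4% and 7% at SD 5, 93% and 98% at SD 8, and 10% and 17% at SD 6.4 with a mean improvement of 2 points. It also measures how strict that row is, not the harm from the wording, so nothing here rests on it.

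Finally, it would be too strong to say that surface findings can never count. The corneal depithelization row refers to the ocular surface, and conjunctival hyperemia has limits in 14.2.1.

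**Conclusion.** The point holds as a defect in the decision rules as written. Two rules reach the same verdict from different tables, one cites the efficacy table, and no rule concludes on safety although that is a stated objective. Opposite verdicts follow from as few as five subjects per arm. The probabilities of 0.84 to 0.98 rest on assumed rates for one parameter and show only that the conflict would be common under modest improvement; the contradiction itself needs no such assumption beyond the reading of *changes* given above. The list-and-table mismatch is real but secondary: one item on each side, with OSDI already counted and ocular surface lacking its own row. The plan should be corrected. The defect does not threaten the data, and the likely intent can be recovered from the text.

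**What to change.** All changes are to wording in section 14.

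1. In the 14.2 rule, change the cross-reference from 14.1.2 to 14.2.1. Without this, improvement would still count against tolerability whatever else is corrected. Once 14.2.1 governs, note that pruritus is in the 14.2 list but has no row there.
2. In the safety rule, change *tolerable* to *safe*, so that 14.2 concludes on tolerability and the safety rule on safety. The table of contents gives 14.2 as safety and 14.3 as tolerance, the reverse of the body, and should be aligned.
3. Add OSDI to the safety list, to match table 14.3.1.
4. Reconcile ocular surface with the table in one of two ways. Either map it to the existing corneal depithelization row, which at present speaks of a reduction in staining and would need to describe worsening. Or add a row for worsening of the bulbar and tarsal hyperemia grades, which section 10.3.3 already collects, with a criterion set by the sponsor. Chemosis is less suitable, because the protocol evaluates it but gives no grading scale.

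The cost is small: no new visit, procedure or subject. If a surface row is added, the safety verdict may become slightly harder to pass, and hyperemia would then appear under both tolerability and safety, so the two criteria should be worded to be compatible.

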5. OSDI
6. Goblet cells population

It is considered that the drug in evaluation PRO-087 is effective for use in patients diagnosed with mild to moderate tear film dysfunction, if they exhibit the changes marked in parameters (14.1.2) by more than 5% of subjects in both eyes, in compliance with all visits and adherence to treatment at an 80% during the time of study assessment.

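### Read literally, the 5% safety rule leaves out a change confined to one treated eye, and no other section sets the unit of count

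*Combined protocol and SAP*

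**What the plan says.** Section 14 has three pass rules, each built on 5% of subjects and a reference to both eyes.

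- **Safety** (printed after the table in 14.2.1): PRO-087 is tolerable "if there are not changes on the marked parameters (14.3.1) by more than 5% of subjects, in both eyes". The subjects considered are those "in compliance with all visits and adherence to treatment at an" 80% level or higher.
- **Tolerability** (14.2): tolerable "if there are no changes on the marked parameters (14.1.2) by more than 5% of subjects, in both eyes". Section 14.1.2 is the efficacy table. The tolerability table is 14.2.1, where burning, foreign body sensation, tearing and secretion each carry the limit "It should be recorded as absent on 95% of the evaluated subjects", and hyperemia and photophobia have graded limits. None of these limits mentions eyes.
- **Efficacy** (14.1): the drug is effective if the changes are shown "by more than 5% of subjects in both eyes".

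Most safety parameters in 14.3.1 are findings in a single eye. Examples are "Measurements below 7 mmHg and over 21 mmHg" for intraocular pressure, "Abnormalities on any of the comprised structures: Cornea, iris, pupil, iris-corneal angle and crystalline" for the anterior segment, a one-line acuity change, and a fall of more than 20% in TBUT or Schirmer. OSDI and adverse events in the same table belong to the subject. Neither 14.3.1 nor the statistical analysis in section 15 gives an either-eye, worst-eye or per-eye rule.

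**The concern.** In a rule about benefit, asking for the change in both eyes is the demanding direction. In a rule about harm, the same words work the other way: a subject with pressure above 21 mmHg in one eye and a normal fellow eye does not have the change in both eyes, and so drops out of the numerator.

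This sentence is the only stated threshold for the safety verdict. If it is applied as written, PRO-087 can pass while well over 5% of subjects have a listed change in a treated eye. If it is treated as open to interpretation, the counting unit is left to be chosen after the data have been seen.

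**Working it through.** The plan gives no figure for this rule, so there is none to reproduce. The question is how far the verdict depends on the unit of count.

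**Inputs from the plan**
- Limit: more than 5% of subjects fails (safety rule after 14.2.1).
- Subjects per group: 80 before losses and 80 × 1.20 = 96 after (13.3). I take both as given. Because the rule considers only subjects who attend every visit and adhere, the true denominator may be nearer 80.
- Largest passing count: 5% of 96 is 4.8, so 4 passes (4.2%) and 5 fails (5.2%). With 80, 4 subjects is exactly 5.0% and still passes.

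**Assumed, not in the documents**
- p, the risk that a given eye meets one criterion, and r, the correlation between the two eyes of a subject.
- One parameter at a time, with subjects independent.

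**Formulas**
- Both eyes affected: B = p² + r·p·(1 − p)
- At least one eye affected: E = 2p − B
- Chance of passing: probability that a binomial count (96 or 80 subjects, with probability B or E) is 4 or fewer.

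**Worked case, p = 5%, r = 0.3**
- B = 0.0025 + 0.3 × 0.05 × 0.95 = 0.01675, or 1.7% of subjects
- E = 0.10 − 0.01675 = 0.08325, or 8.3% of subjects

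| p | r | Subjects | Both eyes affected | Either eye affected | Pass, both-eyes count | Pass, either-eye count |
|---|---|---|---|---|---|---|
| 1% | 0.3 | 96 | 0.3% | 1.7% | 100% | 98% |
| 2% | 0.3 | 96 | 0.6% | 3.4% | 100% | 78% |
| 5% | 0.3 | 96 | 1.7% | 8.3% | 98% | 9% |
| 5% | 0.3 | 80 | 1.7% | 8.3% | 99% | 19% |
| 10% | 0.3 | 96 | 3.7% | 16.3% | 72% | under 0.1% |
| 5% | 0 | 96 | 0.25% | 9.75% | 100% | 4% |
| 5% | 0.7 | 96 | 3.6% | 6.4% | 74% | 25% |
| 5% | 1 | 96 | 5% | 5% | 47% | 47% |

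At p of 1% or 2% with r = 0.3, fewer than 5% of subjects are affected in either eye, so a pass is the right answer on both counts. The two counts lead to opposite conclusions when B is below 5% and E is above it, as in the 5% and 10% rows with r below 1.

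**A third reading.** Suppose the sentence means that neither the right-eye nor the left-eye percentage may exceed 5%. Four subjects affected on the right and four others on the left would then pass, which is 8 of 96 subjects, or 8.3%. In rates, two values just under 5% allow just under 10% of subjects with an affected eye.

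**The case against.** The strongest reply is that the sentence is negative. Requiring no change in both eyes can mean that each eye must be free of change, which is the same as counting either eye. The efficacy sentence does not settle the matter, since its wording is equally undefined. This stands: the lenient reading follows the plain word order but is not the only one. It does not rescue the rule, because no section selects the strict reading and the per-eye reading is lenient too.

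A second reply is that the illustration rests on assumed risks. That is correct. With rare events the choice hardly matters, and with perfectly bilateral events it does not matter at all.

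A third is that requiring both eyes guards against measurement noise. Take a baseline Schirmer of 8 mm (assumed), no true change, and the 1.72 mm SD of section 13.3 treated as the SD of change. A fall above 20% is then more than 1.6 mm, and 1.6 / 1.72 = 0.93 SD, which about 18% of eyes exceed by chance at one visit. With independent eyes that is 32% of subjects in either eye (1 − 0.824²) and 3% in both (0.176²). The point has weight for Schirmer, but the plan gives no such reason, and the same phrase also covers pressure and structural abnormalities.

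Three stronger inferences are tempting but not supported:
- *One-eye harm is lost from the trial.* Section 18 requires all adverse events to be reported, and section 17.4 keeps the data of withdrawn subjects for safety analysis.
- *A one-eye corneal ulcer escapes because of this phrase.* Ulcer is an elimination criterion in 12.2.3, so the all-visits condition could remove that subject whether one eye or two is affected.
- *The tolerability verdict is biased in the same way.* The 14.2.1 limits apply to subjects with no eye condition, and the 14.2 sentence cites the efficacy table. The fault there is a wrong cross-reference and a phrase that conflicts with its own table.

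**Conclusion.** The concern holds for the safety rule. Read literally, a change in one treated eye does not count toward the 5% limit. A strict reading is possible, but nothing in the plan adopts it. The rule can therefore give a wrong verdict, which goes beyond a missing detail.

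The size depends on per-eye risk and between-eye correlation, which the documents do not give. At 5% per eye and correlation 0.3, the pass chance is 98% against 9% with 96 subjects, and 99% against 19% with 80. It is 100% against 78% at 2% per eye, 100% against 98% at 1%, and equal at correlation 1. The defect is confined to the verdict and does not affect data capture. For tolerability, the finding is only that the sentence and its table must be made to agree.

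**What to change.** 1. In the safety rule after 14.2.1, replace the both-eyes phrase with *in at least one treated eye* for the eye-level parameters of 14.3.1. Count each subject once per parameter, at the visits where that parameter is scheduled. Keep OSDI and adverse events at subject level.
2. In 14.2, change the cross-reference from 14.1.2 to 14.2.1 and delete the both-eyes phrase, so that the sentence matches the subject-level limits in the table.
3. Leave the efficacy rule in 14.1 as a separate matter.

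Make the change before unblinding. It needs no new examination, but the visits that count for intraocular pressure must be reconciled: the section 9 schedule and section 10.3.8 place it at the baseline and final visits only, while sections 11.2 to 11.4 also list it at visits 1 to 3.

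The cost is a less favourable observed safety percentage. Variable measures such as Schirmer will also exceed 5% by chance more often, as the illustration above shows.

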#### 7.5 *Allocation to intervention groups*

The allocation to the study groups will be held in the visit outlined in the study schedule, randomly, through a specialized software that uses random number tables to achieve a uniform allocation in each intervention group.

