### 13.3 Schirmer

The sample size was calculated according to the formula for continuous quantitative variables:

With a statistical confidence level of 95%, which corresponds to the error type I, and is equal to 1.96, with a potency of 80% corresponding to the error type II, and is equal to 0.84, a standard deviation for the 1.72 mm/5 min increase in the Schirmer test, with an expected difference of at least 0.13 mm/5 min, was considered.

Based on the above, the result was 80 patients, which increased 20% in consideration of the losses, with a total of 96 patients per group, with total study population of 288 subjects (576 eyes).

Based on the above calculations and considering the primary outcome variable, and Schirmer test used in the study to demonstrate efficacy between the 3 groups, the total population to evaluate will be of 288 subjects.

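### The 5% tolerability rule is judged on the observed percentage, so a pass does not show that serious adverse events or segment abnormalities occur in fewer than 5% of subjects

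*Combined protocol and SAP*

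**What the plan says.** The safety rule stands in the paragraph that follows the tolerability table in section 14.2.1. It calls PRO-087 tolerable "if there are not changes on the marked parameters (14.3.1) by more than 5% of subjects", with the qualification "in both eyes, in compliance with all visits and adherence to treatment at an" level of at least 80%.

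Table 14.3.1 lists the parameters. Beside falls of more than 20% in TBUT and Schirmer, it contains:

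- an adverse-event row: "Presence of adverse events modifying some of the abovementioned criteria or others evaluated as serious";
- an anterior-segment row: "Abnormalities on any of the comprised structures: Cornea, iris, pupil, iris-corneal angle and crystalline";
- a posterior-segment row: "Abnormalities on any of the comprised structures: Vitreous, retina, macula and optic nerve".

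None of these three rows has a limit of its own. In the table of section 14.2.1, by contrast, conjunctival hyperemia and photophobia have graded limits, and the serious grade of each is capped at 1.0%.

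On numbers, section 13.3 states that "the result was 80 patients, which increased 20% in consideration of the losses, with a total of 96 patients per group" and that "the total population to evaluate will be of 288 subjects". Section 15 plans frequencies, and chi-square or Fisher tests between groups. It plans no confidence interval or upper bound on a safety rate, and it does not tie the tests to the 5% rule.

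**The concern.** A tolerability verdict will be read as a statement about the product and not only about the subjects in this trial. If the observed percentage alone decides it, the verdict carries no allowance for sampling error. Section 13 sizes the trial on TBUT, OSDI and Schirmer means, so nothing in the plan ensures that a rate near 5% is estimated well enough to support the verdict.

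The plan's own limits are also out of order. A serious grade of hyperemia is held to 1.0%, while an adverse event rated serious, or an abnormal retina or optic nerve, shares the 5% given to a drop in TBUT. At stake is the wording of the safety conclusion: it could be favourable on data that do not exclude rates about twice the stated limit.

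**Working it through.** **Inputs.** The limit is 5% of subjects, and exactly 5% passes (section 14.2.1, safety paragraph). Section 13.3 gives 80 subjects per group, raised for losses to 96. The plan's steps reproduce: 80 × 1.2 = 96 and 96 × 3 = 288, with equal groups as section 7.5 intends ("random number tables to achieve a uniform allocation in each intervention group"). The 80 does not follow from the Schirmer inputs, since 2 × [(1.96 + 0.84) × 1.72 / 0.13]² ≈ 2,745. That is a separate matter; here 80 and 96 serve only as the planned denominators.

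**Step 1: largest count that passes.** This is the largest k with k/n ≤ 0.05.

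- n = 80: 4/80 = 5.0% passes.
- n = 96: 4/96 = 4.2% passes; 5/96 = 5.2% fails.
- n = 60 to 79: 0.05 × 60 = 3.0 and 0.05 × 79 = 3.95, so k = 3.

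**Step 2: what a borderline pass shows.** The exact (Clopper-Pearson) one-sided 95% upper bound is the 0.95 quantile of Beta(k + 1, n − k).

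- 4/80: 11.1%.
- 4/96: 9.3%.
- 3/79: 9.5%.

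**Step 3: how often the rule passes.** For one parameter and X ~ Binomial(n, p), the chance of a pass is P(X ≤ 4).

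| True rate p | n = 80 | n = 96 |
|---|---|---|
| 2% | 0.98 | 0.96 |
| 3% | 0.91 | 0.84 |
| 5% | 0.63 | 0.47 |
| 8% | 0.22 | 0.11 |
| 10% | 0.09 | 0.03 |

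Passing at 2% or 3% is what a 5% limit should do. The difficulty lies at and above the limit. At a true rate of exactly 5% the rule passes about half the time, and at 8% it still passes in 22% or 11% of trials.

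**Step 4: the 1.0% tiers.** Counted by subject, one case is 1/80 = 1.25% or 1/96 = 1.04%. Both exceed 1.0%, so no subject is allowed. With zero cases the one-sided 95% bound is 1 − 0.05^(1/n), which is 3.7% at n = 80 and 3.1% at n = 96. Counted by eye, 96 subjects give 192 eyes and one eye is 1/192 = 0.52%, which passes. The tiers do not say which unit applies.

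**Step 5: what a bound-based rule would ask.** Suppose, for illustration, that the one-sided 95% bound itself had to be at most 5%. At n = 80 only zero cases would pass (one case gives 5.8%). At n = 96 one case would pass (4.85%). Accepting four cases would need 181 subjects.

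**Step 6: who is counted.** The rule is tied to subjects who attend every visit and adhere at 80% or more. Section 18.1.1 interrupts the drug after a serious event derived from it, and section 12.2.3 eliminates subjects with, for example, corneal ulcers or uveitis. Such subjects may drop out of the set on which the verdict is taken, although section 17.4 keeps withdrawn subjects' data for safety analysis. The both-eyes condition could also leave a one-eye finding uncounted.

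**The case against.** The strongest reply is that the criterion is descriptive. The neighbouring tolerability table speaks of what is recorded, and nowhere does the plan claim that a true rate is bounded. Safety is also handled elsewhere: all events are reported (18.4), causality is coded (18.5), serious events go to the sponsor within 24 hours and also to ethics committees and authorities (18.5.6), and section 15 compares groups. The rule also usually rejects high rates, with a pass probability of 9% or 3% at a true rate of 10%. All of this is correct, but none of it changes the rule by which the product is called tolerable.

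Four stronger readings are tempting, and the documents do not support them.

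- *That PRO-087 could pass while causing serious harm.* Section 18.1.1 defines an adverse event without requiring a causal link, and section 18.2.1 counts a hospitalisation as serious. In adults up to age 90, four such events need not come from the drug. The adverse-event row may even mean severe intensity, because section 18.2.2 uses the same word for the top severity grade.
- *That structural eye damage is tolerated.* The table says abnormalities. It does not require damage, new onset or relation to the drug.
- *That each row has its own 5%.* The rule does not say whether the limit applies per parameter or to subjects with any change. Some rows, such as visual acuity and corneal staining, are not worded as harms and cannot be applied literally. Four affected subjects pass under either reading if nothing else fails.
- *That the 1.0% tiers are simply a zero-event rule.* That holds only if they are counted by subject.

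**Conclusion.** The point holds in this form: the tolerability rule rests on an observed percentage, applies one 5% allowance to adverse events rated serious and to segment abnormalities without a limit of their own, and asks for no precision. Four affected subjects among 80 to 96 pass, and that result is compatible with a true rate of up to 11.1% or 9.3%. A pass therefore cannot be read as showing a rate below 5%, and it says nothing either way about causation.

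The figures assume that the denominator is the PRO-087 group, that 80 to 96 of its subjects meet the visit and adherence conditions, that cases are independent between subjects, and that one parameter is judged at a time. If 60 to 79 qualify, the allowance is 3. The statement about the 1.0% tiers also assumes counting by subject. This should be corrected before the safety conclusion is written, but it does not stop the trial from running.

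**What to change.** 1. Beside each percentage limit, report the exact one-sided 95% upper bound for PRO-087, and word the tolerability conclusion on that bound (for example, 4 of 96 observed, upper bound 9.3%).
2. Do not let the 5% allowance alone settle the adverse-event and segment rows. Report each serious event and each new abnormality by arm, with the causality that section 18.5 already collects.
3. State whether the 1.0% tiers count subjects or eyes, and give the bound that the chosen denominator supports. If by subject, that is zero allowed, with a bound of 3.7% at 80 or 3.1% at 96.
4. Reconcile the compliant-only wording of the safety rule with sections 17.4 and 18.1.1, so that subjects stopped for a serious event are counted in the verdict.

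The cost is revised wording in section 14, a matching line in section 15, and a small amount of extra analysis. No new subjects or data are needed. The downside is a safety statement that reads less favourably than a bare within-5% result.
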